# 5.2 Study Evaluations

### 5.2.1 Screening/Baseline Evaluations (Visit 1, Day -28 to -1)

The beginning of the screening period per subject is defined by the date of written consent. Screening and baseline assessments (Visit 1) will be performed as close as possible to inclusion and all results will be available for inclusion. The Investigator will complete the inclusion checklist prior to enrolling the patient in the trial. Results of any tests available apart of routine care, which may have been performed by the referral hospital within the specified time window but prior to informed consent, do not need to be repeated.

The following screening/baseline evaluations are performed to determine the subject's eligibility for study participation and for determination of the baseline status:

- Check of Inclusion/Exclusion criteria
- Medical History
- Recording of demographic and medical history
- Completion of Quality-of-life questionnaire (Appendix 0)
- Completion of Lymphatic side effects questionnaire (Appendix 12.2)

For a detailed description of the assessments, please see section 5.3.

Patients meeting the inclusion criteria and not fulfilling the exclusion criteria will be randomized to one of the treatments arms at visit 2 (day -28 until -1). It is not necessary for the subject to be present at visit 2.

Each subject must be comprehensively informed about the clinical trial and must give her/his written consent before inclusion in the clinical trial.

A subject who has given informed consent and failed to meet all inclusion criteria and/or meet at least one exclusion

criterion is defined as a screening failure.

# 5.2.2 Enrollment (Visit 2, Day -28 to -1)

Permuted block randomization will be performed with randomly selected block sizes stratified by:

- tumor size (<2cm vs 2-<4 cm)
- sentinel node mapping only (Yes vs No)
- radical vs simple hysterectomy (SHAPE criteria)
- anticipated type of minimally invasive surgery (laparoscopic vs robot-assisted)
- center

Randomization will only be performed after verification of the patient's eligibility and signed written informed consent. All inclusion criteria and no exclusion criteria must be met. Furthermore, baseline assessment of quality of life questionnaires will be performed prior to randomization.

Please note: if a simple hysterectomy is to be considered for patients with low-risk early-stage cervical cancer this must already be determined before the randomization process.

Patients will be allocated to both treatment arms in a 1:1 ratio. Patients will be randomized using the electronic randomization tool provided within the electronic case report form (eCRF)/electronic data capture (EDC) system.

In addition, the following evaluations are performed:

- Collection of urine sample for biobank (first void urine, self-collected by patient)
- Collection of pap smear from cervix (thin prep)

## 5.2.3 Treatment Visit (Visit 3, Day 0)

After enrollment in the trial and randomization in one of the treatment arms the surgery takes place at visit 3 (day 0). The duration of the surgical intervention per participant depends on individual circumstances and will take between 150 and 300 minutes. The surgical procedure is recorded and the sentinel lymph node localized. For a detailed description of the treatment procedure please see section 4.1. In addition, the following evaluations are performed:

Before surgery and desinfection:

- Collection of blood for biobank
- If not done at visit 2: Collection of urine sample for biobank (first void urine, self-collected by patient)
- If not done at visit 2: Collection of pap smear from cervix (thin prep)

During/after surgery:

- Record surgical procedure performed and localization of sentinel lymph node
- Record of intraoperative complications
- Collection of tumor material (if available) and lymph node specimens

• Recording of serious adverse events

# 5.2.4 Follow Up Visits

The Follow Up period begins with visit 4 (1 month after surgery +/- 7 days) and lasts for at least 5 years. Completed assessments will be collected either in connection to the visit at the clinic, electronically (eCRF) or per conventional mail.

The following evaluations are performed during the Follow-up period:

- Length of stay (visit 4)
- Recording of post-operative complications (visits 4–6)
- Recording of pathology of the uterus (visit 4) \*
- Record of adjuvant treatment (if applicable, visit 6)
- Quality of life questionnaire (visits 4–10)
- Lymphatic side effects questionnaire (visits 4–8)
- Record of recurrence (if applicable, visits 5–10)
- Adverse events (visits 4–8)

\* Tumor size assessment in case of prior LEEP/cone excision should be estimated according to the College of American Pathologists (CAP). In providing the final tumor dimensions, the measurements in any prior specimens, for example LEEP/cone excision, will need to be taken into account. Although it may overestimate the maximum horizontal extent, it is recommended to add together the maximum lateral measurements in different specimens when calculating the final horizontal extent. For a detailed description of the assessments, please see section 5.3.

### 5.3 Assessments

### 5.3.1 Informed Consent

Each subject must be comprehensively informed about the clinical trial and must give her/his written consent before inclusion in the clinical trial. The investigator should explain that trial participation is voluntary and that withdrawal from the trial is possible without any disadvantages to the patient's further treatment at any time and for any reason. The patient information/informed consent form has to be signed by the patient and the investigator. One document (may be a copy) will be given to the patient, the other remains at the trial site. No study procedures are allowed to be conducted until patient's signed and dated informed consent has been obtained. It is planned to collect biomaterials during the study at pre-defined time points. Patients will be asked at study inclusion to give separate (independent of participation in the primary interventional trial) informed written consent before collection of biomaterials.

## 5.3.2 Eligibility Criteria

The investigator will assess patients for eligibility at the screening visit after the written informed consent has been obtained. Patients eligible for trial participation have to meet all of the inclusion criteria and none of the exclusion criteria (for details see section 3.2 and 3.3).

#### 5.3.3 Demographics and Medical history

Demographic data and medical history will be recorded at screening/baseline visit (visit 1) after written and oral informed consent was obtained. Demographic data includes gender, year of birth, height, weight and ethnic origin. For medical history please record the following data: FIGO stage (IA2, IB1 or IB2), preoperative LEEP/cone excision (yes/no). In case of preoperative LEEP/cone excision, please record: histology according to cone excision (primary adenocarcinoma, squamous cell carcinoma or adenosquamous carcinoma), tumor size (horizontal extent in mm), depth of invasion (in mm), tumor grading (G1-G3), ECOG performance status (0 or 1).

#### 5.3.4 Record surgical procedure performed and localization of sentinel lymph node

Hospital:	City:			Country:		
Date of surgery:	, ,			,		
Surgical approach according to randomization:	Laparoscopic/robot-assisted approach		Abdominal approach			
Operation time (skin to skin):					minutes	
Estimated blood loss:					ml	
Transfusion	Yes -> Number o	of erythrocyte	concentrates	no		
Simple or type of radical hysterectomy according to Querleu-Morrow classification:	Simple	B1	B2		C1	
Complete/radical lymphadenectomy performed	complete lef	t side		complete right s	side	
Sentinal lymph node procedure only?	yes			no		
Localisation of sentinel lymph nodes:	left common	iliac		right common il	iac	
	left external			right external iliac		
	left internal	iliac nodes		right internal iliac nodes		
	left obturato	r fossa		right obturator fossa		
Type of uterus manipulator:						
Vaginal closure before colpotomy?	Vaginal cuff					
(Indicate method)	Stapler					
	Sling					
	Other					
	None					
Salpingectomy:	yes			no		
Oophorectomy:	yes			no		
Transposition of ovaries:	yes			no		
Nerve sparing surgery:	yes			no		
Conversion to open surgery:	yes			no		
Intraoperative complications - indicate what kind	yes			no		
Organ injury (please indicate below):						
Urinary Bladder:	yes			no		
Ureter:	yes			no		
Small Bowl:	yes			no		
Colon:	yes			no		
Blood vessel:	yes			no		
Nerve:	yes			no		
Other (please mention):	yes			no		

#### 5.3.5 Record intraoperative complications

Please record intraoperative complications according Rosenthal classification (see Appendix 12.1 for further information).

## 5.3.6 Length of stay

Please record the number of days spent in hospital.

#### 5.3.7 Record post-operative complications

Please record post-operative complication and state if any of the following adverse events occurred: abdominal pain, constipation, fatigue, paresthesia, peripheral sensory neuropathy, urinary incontinence, urinary retention, dyspareunia, pelvic pain, lymphedema, hot flashes.

#### 5.3.8 Follow-up care according to national guidelines

Please record if a Follow-up care according to national guidelines has been performed. Follow-up care includes physical examination and medical consultation among other optional procedures (e.g. tumor marker or cytology).

## **5.3.9** Record pathology of the uterus

Please state the pathology report of the uterus as given from the pathology department of your institution. The report should include tumor type, tumor horizontal extent, depth of invasion, grading, presence of lymph vascular involvement (L-Status), presence of vascular involvement (V-Status) perineural invasion (Pn-Status), parametria (left and right in mm), nodal status (number of positive sentinel lymph nodes out of total sentinel lymph nodes for left and right pelvis; number of positive lymph nodes out of total lymph nodes; number of positive paraaortal lymph nodes out of total paraaortal lymph nodes), presence of micrometastasis and presence of isolated tumor cells.

Tumor size assessment in case of prior LEEP/cone excision should be estimated according to the College of American Pathologists (CAP). In providing the final tumor dimensions, the measurements in any prior specimens, for example LEEP/cone excision, will need to be taken into account. Although it may overestimate the maximum horizontal extent, it is recommended to add together the maximum lateral measurements in different specimens when calculating the final horizontal extent.

State the final estimated tumor size (in mm), final estimated depth of invasion (in mm) and final TNM status.

#### 5.3.10 Record adjuvant treatment

Adjuvant treatment of patients is recommended according to national guidelines. Please record the adjuvant treatment. E.g. adjuvant post-operative treatment (Yes/No), chemotherapy only (Yes/No), radiation therapy (Yes/No), chemoradiation (Yes/No).

## **5.3.11** Biosampling (Collection of biomaterials)

An optional translational research component is included within the study. Prospectively collected blood and tumor samples will be collected from the participating centers. Additionally, already processed tumor material can be requested from the individual pathological departments.

These biomaterials will be used to enable accompanying scientific projects related to the treatment of cervical cancer in the future. Biomaterials will only be collected if the patient agrees to these procedures and signs a separate consent for the collection of biomaterials.

Tumor material will be collected during surgery (visit 3) to allow correlation of molecular tumor characteristics with clinically relevant endpoints. Hysterectomy and lymph node specimens will be collected at visit 3 and processed

according to the current valid German S3 guideline  (or national equivalent) and sections 4.1.1 and 4.1.2. In addition, blood samples will also be collected at visit 3 and pap smear from cervix (thin prep) as well as urine samples will be collected either at visit 2 or at visit 3 (see section 5.1).

A subject-ID will be assigned which will also be documented in the screening and enrollment log. It is composed of two digits for the site and 3 digits for the sequential number of the patient in the site, e.g. 02-004. Biomaterials will be labeled with the subject ID as well. The following abbreviations will be used: B = blood sample, T = tumor material, P = pap smear/ smear from cervix (thin prep), U = urine. The final label will be composed as follows: **CENTER (\_\_)\_ Randomization Number (\_\_)\_ BIO\_Visit No.\_ Material (T = Tumor/L = Lymph/B = Blood/P = Pap Smear/U = Urine)** 

e.g. 01\_001\_BIO\_1\_T, indicating a probe from: center 1, randomized patient 1, drawn at visit 1, Tumor material. Furthermore, registration data has to be entered to an electronic Case Report Form (eCRF).

The aims of the translational studies are to evaluate and validate novel prognostic and predictive biomarkers for lymph node metastasis, recurrence and survival. The investigated biomarkers will be correlated with clinically relevant endpoints. Additionally, biomaterials will be analyzed with regard to structure and composition of the immunological tumor microenvironment and the expression level of biomarkers that represent promising targets for cellular immunotherapy. Adoptive immunotherapy will play a major role in future therapeutic strategies for cervical cancer and large collections of biomaterials are missing. In selected cases viable tumor material will be collected to generate cell models to investigate novel immunotherapeutic approaches against cervical cancer.

## 5.3.12 Quality of Life Assessments

In order to compare the grade of short- and long-term effects on the patients' HRQoL between both treatments (ARH und LRH) all participants will be asked to complete QoL questionnaires at different times over the course of the trial. The QoL assessments' focus will be on late side-effects such as bladder dysfunction, sexual activity, physical-, emotional, and role functioning as well as fatigue and pain.

Patients will complete HRQoL questionnaires in an appropriate language either as electronical patient reported outcome measures or during the clinic visits (by manually filling in hardcopy forms, by accessible computer (eCRF) or by mail). Study personnel, e.g. investigator or study nurses, will not have access to the QoL-forms while answered by the patient in order to avoid any influence.

Eligible patients will be informed orally and in writing about the HRQoL assessment before inclusion in the trial. Baseline assessment will be performed before randomisation to one of both treatment arms at visit 1 but only after written and oral informed consent is obtained. Post-surgery assessments will be conducted 1 and 6 months as well as 1, 2, 3, 4 and 5 years after treatment at visits 4 to 10 (see section 5.1). Completed questionnaires will be collected either in connection to the visit at the clinic, electronically via eCRF or per conventional mail and are always considered as source documents.

The following questionnaires will be completed by all patients included in the G-LACC trial as stated above (see Appendix 0):

#### EORTC QLQ-C30

The European Organization for Research and Treatment of Cancer Quality of Life Questionnaire-C30, version 3.0 (EORTC QLQ-C30) is a questionnaire developed to assess the quality of life of cancer patients participating in clinical trials and has been used in a wide range of cancer trials and by a large number of research groups. The EORTC QLQ-

C30 is composed of both multi-item scales and single-item measures. The nine multi-item scales include five functional scales (physical, social, role, cognitive and emotional), three symptom scales (fatigue, nausea/vomiting and pain) and an overall health status / QoL. Each of the multi-item scales includes a different set of items - no item occurs in more than one scale. The six single-item scales include dyspnea, sleep, disturbances, appetite loss, constipation, diarrhea and financial impact.

#### EORTC QLQ-CX24

The EORTC QLQ Cervical Cancer Module (CX-24) is a cervical cancer specific questionnaire developed to assess the quality of life of women with cervical cancer participating in clinical trials. The EORTC QLQ-CX24 is composed of 24 items divided into four functioning scales (body image, sexual activity, sexual enjoyment and sexual/vaginal functioning) and five symptom scales (symptom experience, lymphoedema, peripheral neuropathy, menopausal symptoms, sexual worry).

#### EuroQol EQ-5D-3L

The EuroQol EQ-5D-3L is a questionnaire to assess the health-related quality of life in clinical trials and real-world clinical settings not specific to any patient group or health condition. The EQ-5D-3L comprises a descriptive system part and visual analogue scale. The descriptive system consists of five dimensions (mobility, self-care, usual activities, pain/discomfort and anxiety/depression) with three levels each (no problems, some problems or extreme problems). The 20 cm visual analogue scale records the patient's self-rated health where the endpoints are labeled with 100 (best imaginable health state) and 0 (worst imaginable health state).

#### SAQ (Sexual Activity Questionnaire)

The Sexual Activity Questionnaire (SAQ) is a patient self-administered tool to assess the impact that any treatment may have on sexual functioning. The SAQ has been used in several clinical trials of gynecological diseases and is divided into three sections focusing on the relational, emotional, and behavioral characteristics of sexual activity.

## 5.3.13 Lymphatic side effects

Lymphatic side effects with specific assessment for lymphatic and lower limb complications will be conducted by both, the investigator and the patient. The investigator will assess lymphatic side effects according to the Common Terminology Criteria (CTC) version 3.0 , patients will complete the LYMQOL questionnaire  (see Appendix 12.2) in an appropriate language either as electronical patient reported outcome measures or during the clinic visits (by manually filling in hardcopy forms, by accessible computer or by mail) and are always considered as source documents. Study personnel, e.g. investigator or study nurses, will not have access to the LYMQOL-form while answered by the patient in order to avoid any influence.

Baseline assessment will be performed before randomization to one of both treatment arms at visit 1 but only after written and oral informed consent is obtained. Post-surgery assessments will be conducted 1 and 6 months as well as 1, 2, 3, 4 and 5 years after treatment at visits 4 to 10 (see section 5.1). Completed assessments will be collected either in connection to the visit at the clinic, electronically or per conventional mail and are always considered as source documents.

## LYMQOL

The Lymphoedema Quality-of-Life Questionnaire (LYMQOL) is a validated disease-specific tool which was developed to measure the impact of lymphoedema on patients' quality of live. The LYMQOL needs to be completed only if the

patient reports that she has lymphedema. The LYMQOL questionnaire assesses the impact of lymphoedema on several aspects of the patient's life and covers four domains (symptoms, body image/appearance, function and mood).

#### **5.3.14** Record if recurrence

In addition to the follow-up visits as scheduled in the study calendar (see section 5.1), patients will receive followup care according to national guidelines. Follow-up care includes physical examination and medical consultation among other optional procedures (e.g. tumor marker or cytology). In case of abnormal findings during follow-up or clinical suspicion of disease recurrence, imaging diagnostic should be performed. Recurrence of disease must be verified by histopathological assessment. The date of biopsy counts as the date of recurrence. State where the recurrence occurred:

- Type of analysis (CT, MRT, Biopsy, other)
- pelvic recurrences (vaginal vault, parametrium, pelvic lymph nodes, or other)
- extra pelvic recurrences (abdomen, para-aortic lymph nodes, supraclavicular lymph nodes, or other)
- if possible, an additional blood sample should be collected

#### 5.3.15 Safety assessments (intra-/post-operative complications, SAEs)

Treatment related intra-operative complications will be recorded on the day of surgery (visit 3) according to the definition of Rosenthal (see Appendix 12.1).

Treatment related post-operative complications will be recorded starting directly after surgery up to one year thereafter with a first assessment 30 days post-surgery (visits 4 to 6).

Furthermore, other particularly not treatment related serious adverse events (SAEs) will be captured from the day of surgery until one year post surgery (visits 3 to 6). For a detailed definition of SAEs and the recording procedure see sections 6.1 and 6.2. Note that the reporting of all serious adverse events is mandatory for the investigator within 24 hours after awareness (see section 6.2).

SAEs have to be reported in the eCRF. Serious adverse events will be reported anually to the Ethics Committee according to the Declaration of Helsinki.

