### 2 STUDY DESIGN AND OBJECTIVES

### 2.1 Study Design

The G-LACC trial is a prospective, interventional, multicenter, open-label, randomized and controlled non-inferiority operative trial.

Eligible patients will be randomly allocated to both treatment arms in a 1:1 ratio. Within an accrual period of 4 years, 378 patients will be included per arm (756 in total) across all sites. The Follow-up period after surgery will take a minimum of 5 years.

[figure not shown]

Figure 1: Study scheme of the G-LACC trial

In the standard arm, radical hysterectomy is performed as per standard technique (abdominal radical hysterectomy (Piver type 2 or 3 or Querleu & Morrow Type B or C) with salpingectomy +/- oophorectomy. Ovaries may be removed or preserved +/- transposition. Surgery includes pelvic lymph node dissection or optional sentinel lymph node biopsy (SNB) according to current guidelines in both arms.

In the experimental arm, radical hysterectomy is performed as per standard conventional 2D/3D laparoscopic or robotic assisted technique (Querleu & Morrow Type B or C) with salpingectomy +/- oophorectomy. Ovaries may be removed or preserved +/- transposition. The following protective measures are mandatory for the minimal-invasive arm: LEEP/conization before randomization or closure of the vagina before colpotomy. Transcervical manipulators are not permitted. Use of uterus manipulators/ cervical adapter (without transcervical device) are allowed only after LEEP/conization. Meticulous dissection of pelvic (sentinel) lymph nodes including use of endobags and avoiding the dissemination of cancer cells will be implemented (tumor hygiene).

Due to the positive results of the SHAPE trial presented at ASCO 2023, in both arms simple hysterectomy can be considered for patients with low-risk early-stage cervical cancer (SHAPE-criteria: tumor < 2 cm, < 10 mm depth of stromal invasion (LEEP/cone) BUT has to be determined BEFORE randomization. Simple hysterectomy has to be performed as extrafascial hysterectomy and the preparation of a max. 5mm vaginal cuff is required to ensure negative margins. Surgery can be performed including removal of the sentinel lymph nodes following the concept of sentinel lymph node biopsy (SNB) and according to the current guidelines.

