### Complications and treatment-associated morbidity

Intra- and post-operative treatment-related complications are recorded. In addition, other serious adverse events (SAEs) are captured at each visit starting with surgery (section 6).

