#### **12 APPENDICES**

#### 12.1 Intra-operative complications

Classification of Intraoperative Complications (CLASSIC) according to Rosenthal et al.

Grade	Definition
	The classification exclusively relates to any event occurring between skin incision and skin closure and should be rated directly after surgery. Any event during the index-surgery must be considered, regardless whether it is surgery or anesthesia-related a .
	Prerequisite: the indication for surgery and the interventions conform to current guidelines
Grade 0	No deviation from the ideal intraoperative course
Grade I	Any deviation from the ideal intraoperative course
	• Without the need for any additional treatment or intervention
Grade II	Any deviation from the ideal intraoperative course
	• With the need for any additional treatment or intervention
	
 
Not life-threatening and not leading to permanent disability
 

Grade III	Any deviation from the ideal intraoperative course
	• With the need for any additional treatment or intervention
	
 
Life-threatening and/or leading to permanent disability
 

Grade IV	Any deviation from the ideal intraoperative course
	• With death of the patient

ENGLISH

Version no.: 2.0; dated 15. May 2024; Short study title: G-LACC

Quality of Life Questionnaires

EORTC QLQ-C30

EORTC QLQ-C30 (version 3)				
We are interested in some things about you and your health. Please answer al number that best applies to you. There are no "right" or "wrong" answers, remain strictly confidential.				
Please fill in your initials:       IIIIIIIIIIIIIIIIIIIIIIIIIIIIIIIIIIII				
5	Not at All	A Little	Quite a Bit	Very Much

 
Do you have any trouble doing strenuous activities, like carrying a heavy shopping bag or a suitcase?
 
	1	2	3	4
2. Do you have any trouble taking a long walk?	1	2	3	4
3. Do you have any trouble taking a short walk outside of the house?	1	2	3	4
4. Do you need to stay in bed or a chair during the day?	1	2	3	4
5. Do you need help with eating, dressing, washing yourself or using the toilet?	1	2	3	4
During the past week:	Not at All	A Little	Quite a Bit	Very Much
6. Were you limited in doing either your work or other daily activities?	1	2	3	4
7. Were you limited in pursuing your hobbies or other leisure time activities?	1	2	3	4
8. Were you short of breath?	1	2	3	4
9. Have you had pain?	1	2	3	4
10. Did you need to rest?	1	2	3	4

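### Sections 2.3.2 and 5.3.15 limit the complication endpoint to treatment-related events, but 5.3.5, 5.3.7 and the cited CLASSIC scale do not, so it is unsettled whether attribution decides what is counted

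*Protocol*

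**What the plan says.** Two groups of statements govern what is recorded as a complication.

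**With a relatedness condition.** The complications paragraph of section 2.3.2 defines the secondary endpoint: "Intra- and post-operative treatment-related complications are recorded". Section 5.3.15 repeats the condition for both periods. For the operation: "Treatment related intra-operative complications will be recorded on the day of surgery (visit 3) according to the definition of Rosenthal". For afterwards: "Treatment related post-operative complications will be recorded starting directly after surgery up to one year thereafter".

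**Without one.** Section 5.3.5 tells sites: "Please record intraoperative complications according Rosenthal classification". Section 5.3.7 tells them: "Please record post-operative complication and state if any of the following adverse events occurred", followed by eleven named events. The surgery form in 5.3.4 asks whether a complication occurred and what kind. Appendix 12.1, the scale that 5.3.15 points to, states: "Any event during the index-surgery must be considered, regardless whether it is surgery or anesthesia-related".

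Outside the complication endpoint, 5.3.15 adds that "other particularly not treatment related serious adverse events (SAEs) will be captured from the day of surgery until one year post surgery". Section 6.2 has the investigator assess causality, but describes this for SAEs only. Section 2.1 states the design: "The G-LACC trial is a prospective, interventional, multicenter, open-label, randomized and controlled non-inferiority operative trial". Section 7.1.3 provides that the other secondary endpoints are compared between arms by statistical test.

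**The concern.** A site can follow 5.3.7 and record an event, or follow 5.3.15 and leave it out because it judges the event unrelated. Either way it complies with part of the protocol. The same event may therefore count at one centre and not at another.

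This conflict sits at data entry, so an analysis plan cannot repair it: a non-serious event that was never entered cannot be restored.

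The endpoint also carries weight. Sections 1.5 and 1.6 name fewer complications among the benefits of minimally invasive surgery, and 1.6 sets them against the oncologic risk. Section 1.4 reports that the LACC trial found no such reduction, so the question is contested. Sections 9.3.3 and 9.5 allow centres to be closed for a high rate of major post-operative complications, so uneven recording could reach site oversight too. Because staff know the arm, a relatedness filter would be applied unblinded wherever it is applied at all.

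**Working it through.** The protocol states no complication rate and no share of complications expected to be unrelated, so there is no figure to reproduce. The check is a comparison of the text, followed by an illustration on assumed inputs.

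**1. Intra-operative events.** Sections 2.3.2 and 5.3.15 require the event to be treatment related. Section 5.3.5 and Appendix 12.1 do not; the appendix takes in surgical and anaesthetic events alike. If anaesthesia is understood as part of the treatment, most of the gap closes. If treatment means the surgical procedure alone, anaesthetic events fall under one rule and not the other. The protocol does not say which.

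**2. Post-operative events.** Sections 2.3.2 and 5.3.15 require relatedness, for one year. Section 5.3.7 does not, and its list includes fatigue, paresthesia, peripheral sensory neuropathy, urinary incontinence, lymphedema and hot flashes. During that year patients may receive adjuvant chemotherapy, radiation or chemoradiation (5.3.10), and the ovaries may have been removed (4.1.1). The protocol does not say whether treatment means the surgical route, the whole operation or adjuvant therapy as well. This is the wider gap.

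**3. Who decides.** No criterion, judge or blinded review is given for the relatedness of complications.

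**4. What could be lost.** Unrelated serious events are still captured as SAEs. Some non-serious ones are caught elsewhere:
- the surgery form (organ injury, blood loss, transfusion, conversion)
- the investigator's CTCAE lymphatic grading (5.3.13)
- the quality-of-life questionnaires (5.3.12)

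The remaining exposure is non-serious events outside those items, and only at sites that filter. Events caught only by those other items would still be absent from the complication count.

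**5. Illustration.** Inputs: n = 378 per arm (section 2.1); an assumed true complication rate p, equal in both arms; assumed shares a and b of events kept as treatment related in the two arms.

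- Recorded rates: p1 = p × a, p2 = p × b. Apparent risk ratio = b / a.
- Chance of a significant difference (normal approximation, two-sided 5%): Φ((d − 1.96·SE0)/SE1) + Φ((−d − 1.96·SE0)/SE1), with d = p1 − p2, SE0 = √(2·p̄(1 − p̄)/n), p̄ = (p1 + p2)/2 and SE1 = √((p1(1 − p1) + p2(1 − p2))/n).

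Example with p = 0.20, a = 0.9, b = 0.8: p1 = 0.18, p2 = 0.16, d = 0.02, p̄ = 0.17. SE0 = √(2 × 0.17 × 0.83/378) = 0.0273. SE1 = √((0.1476 + 0.1344)/378) = 0.0273. The chance is 11.3%.

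| Shares kept (a, b) | Apparent risk ratio | p = 10% | p = 20% | p = 40% |
|---|---|---|---|---|
| 0.9, 0.9 | 1.00 | 5% | 5% | 5% |
| 0.9, 0.8 | 0.89 | 7.8% | 11.3% | 21.3% |
| 0.9, 0.7 | 0.78 | 17.3% | 32.3% | 65.5% |

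With equal shares the ratio is unbiased, but both rates are understated; at 0.9 they are 10% too low in relative terms.

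**The case against.** The strongest reply is that the adjective is loose wording. In 5.3.15 it mainly separates complications from the unrelated SAEs mentioned next. The intra-operative sentence adopts the CLASSIC definition in full, and an operation under anaesthesia is naturally the treatment. Every instruction that a site works from (the study calendar, the surgery form, 5.3.5 and 5.3.7) is free of the filter. Much of this stands: the intra-operative conflict is narrow on that reading, and filtering may never happen. It does not settle the post-operative conflict, because 2.3.2 and 5.3.15 state the condition outright and 5.3.7 omits it.

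The reply also defeats several stronger inferences that a reader might draw:

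- *That unblinded attribution does decide who counts as an event.* The protocol describes no attribution step for complications. It leaves the matter open.
- *That filtered events appear nowhere.* The form, lymphatic, quality-of-life and SAE items catch part of them.
- *That positioning load differs by arm, as exclusion criterion 7 might suggest.* That criterion applies to every candidate and says nothing about arms.
- *That the comparison is biased towards minimally invasive surgery.* No document figure supports unequal filtering or its direction.

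A last objection is that counting every post-operative event for a year brings in effects of adjuvant treatment. That is a real cost of the fix. A separate relatedness item makes it visible but does not remove it.

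**Conclusion.** The inconsistency is real. One secondary endpoint has two recording rules, and the protocol does not say which prevails, who would judge relatedness or by what criterion. It matters most for non-serious post-operative events up to one year and little, perhaps not at all, for intra-operative events if anaesthesia counts as treatment.

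Bias between the arms is a possibility, not a demonstrated fault. It arises only if sites filter, and filter differently by arm. On the assumed inputs above, the chance of a spurious significant difference runs from 5% with equal filtering to 65.5% in the most extreme case shown. That range shows how much depends on unstated quantities and is not an estimate for this trial. Even without bias, centres following different sections would report rates that cannot be compared.

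The primary disease-free survival analysis is not touched. The point merits correction because the change is small and the data, once filtered out at the site, cannot be recovered.

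**What to change.** 1. In the complications paragraph of section 2.3.2, delete the words limiting complications to treatment-related ones. Delete the same condition from both complication sentences in 5.3.15.
2. State that the intra-operative endpoint is any CLASSIC grade I to IV event under Appendix 12.1, and that the post-operative endpoint is complications as recorded under 5.3.7, in both cases regardless of attribution.
3. If relatedness is wanted, collect it as a separate descriptive field judged by the investigator, with adjuvant therapy as one possible cause. State that this field does not decide whether an event is counted.

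The cost is a few words in two sections, one optional field, and slightly more events to enter at sites that would have filtered. Some post-operative events caused by adjuvant treatment will be included in both arms; the separate field allows these to be described.
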